Study procedures and **Error! Reference source not found.** sections of the protocol for detailed information on each procedure and assessment required for compliance with the protocol.

Consented Arm

The investigator may schedule visits (unplanned visits) in addition to those listed in the schedule of activities table, in order to conduct evaluations or assessments required to protect the well-being of the participant. Collection of standard-of-care data will be done for all identified LRTD events in study hospitals and entered into the surveillance databases hosted by the Trusts. This will be conducted by appropriate members of the clinical team, and research team members will only have access to pseudonymised data. Sample collection and interview activities shown in bold below will be undertaken for consented participants only by members of the research team.

Table 1. Comprehensive List of Procedures by Visit for Consented-Arm, Including Visit Windows.

Procedure / Assessment ^a	Screening/ Enrolment Visit ^b	Final Assessment/ Vital Status (Data Collection only)	Convalescent Visit ("Serology Subset" Only) ^e	Mortality Assessment (data collection only)
	Visit 1	Visit 2	Visit 3	Visit 4
	Day 1	Day 30	Day 45	Day 365
Visit Window	Within 48 hours of admission	Day 30 to 45	Day 22 to 60^c	Day 365
Screening (surveillance)	X			
Clinical symptoms	X			
Medical History ^c	X	X	X	
Vaccination History	X		X	
CRB-65 and pneumonia severity (PSI) score	X			
Informed Consent	X			
Eligibility confirmation for embedded study	X			
Patient Interview, including approved questionnaires^f	X		X	
Collect urine specimen	X			

Procedure / Assessment ^a	Screening/ Enrolment Visit ^b	Final Assessment/ Vital Status (Data Collection only)	Convalescent Visit ("Serology Subset" Only) ^e	Mortality Assessment (data collection only)
	Visit 1	Visit 2	Visit 3	Visit 4
	Day 1	Day 30	Day 45	Day 365
Collect upper respiratory tract sample for SARS-CoV-2, RSV and other pathogens^d	X		X ^d	
Collect blood specimen^e	X		X	
Obtain residual (scavenged) standard care specimens from clinical laboratory	X	X	X	
Record SOC respiratory specimen testing results	X			
Record SOC blood culture results	X			
Record SOC chest imaging results	X			
Final acute LRTD Illness Diagnosis		X		
Cardiac complications		X		
Vital Status/Mortality		X		X
Hospitalization duration, readmission, & level of care		X		
Collect Research-related Injuries (RRIs)	X	X	X	

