Vaccination History	X		
CRB-65 and pneumonia severity (PSI) score	X		
Record SOC respiratory specimen testing results	X		
Record SOC blood culture results	X		
Record SOC chest imaging results	X		
Final acute LRTD Illness Diagnosis		X	
Cardiac complications		X	
Vital Status/Mortality		X	X
Hospitalization duration, readmission, & level of care		X	

Abbreviations: SOC = standard of care; UAD = urine antigen detection assay; RSV= respiratory syncytial virus; RRI = research-related injury; CRB-65 = Confusion, Respiratory rate, Blood pressure, 65 years of age and older.

a. At Visit 2, relevant changes to medical history since the last visit will be documented.

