3.2 Secondary outcomes

3.2.1 COVID-19/SARS-CoV-2 infection

1. To estimate the population-based incidence rates of COVID-19-related hospitalizations
2. To describe the proportion of LRTI hospitalizations (overall, standard-of-care pneumonia diagnosis, radiologically confirmed CAP only) attributable to COVID-19, both overall and by age/risk stratification
3. To describe demographics, clinical and epidemiological characteristics and outcomes within COVID-19 LRTI and the different subcategories, both overall and stratified by age/risk
4. To describe mortality rate at 30 days after admission to hospital for COVID-19 LRTI and its subcategories, overall and by age group and risk group status
5. To describe the association between COVID-19 and other respiratory pathogens, including but not limited to *S. pneumoniae*, influenza and RSV, both with co- and super-imposed infection and secondary respiratory infection.
6. To describe the length of hospital stay for COVID-19 LRTI hospitalizations and the proportion of COVID-19 admissions involving an ICU stay.
7. To assess whether *S. pneumoniae* LRTI is associated with more severe COVID-19 clinical outcomes (such as requiring invasive mechanical ventilation) among persons hospitalised with COVID-19 infection.

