7.1.1 V1 data collection

Patients meeting screening criteria will have basic demographic and clinical data collected on an e-CRF after consent. This will involve collection of the following data at visit 1:

- Patient details
- Eligibility checks – inclusion/ exclusion criteria components
- Date of hospitalization, length of stay in hospital
- Demographics (age, gender, race/ethnicity, socioeconomic status estimated by postcode, vaccination [e.g. influenza/ PCV13/PPV23/COVID-19 and date of relevant administration], smoking status, alcohol/drug use)
- Details of present illness (symptoms, date of onset, vital signs on admission to hospital)
 - Used antibiotics/antivirals in the 14 days prior to admission
- Standard-of-care test results
 - Routine biochemistry and haematology test results on admission, including C-reactive protein and NT-proBNP
 - Blood cultures
 - Respiratory microbiology testing, including bacterial (eg, PCR and culture) and viral testing (eg, COVID19, RSV and influenza)
 - Pneumococcal testing (eg, BinaxNOW urine test),
 - Antibiotic resistance results for pneumococcal isolates
 - Sputum Gram stain results
 - COVID-19 testing data collection will include tests from up to 14 days prior to hospitalisation based on patient self-report and medical records
- Hospitalization data:

- Admission hospital
- Dates and time of admission/discharge
- ICU stay (yes/no)
- Number of days in ICU
- Mechanical ventilation and days of ventilator use
- Requirement for new/increased haemofiltration
- Non-invasive ventilation requirement and days of usage
- New York Heart Association (NYHA) Heart Failure Classification, Pneumonia Severity (CRB65 and PSI scores)
- Relevant Medical History and Major Comorbidities
- Rockwood Frailty Score and Charlson Comorbidity Index
- COVID risk behaviours questionnaire, which may include occupation, household structure, inclusion in social bubble and mask wearing

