8.2 Non-consented Patient Outcome measures

The follow-up information should be collected 1 month after enrolment or when the patient is discharged from hospital (whichever occurs later). At day 30 after admission, the following will be assessed and recorded in the CRF:

- Microbiological investigation results
 - Blood cultures.
 - Respiratory microbiology testing, including bacterial (eg, PCR and culture) and viral testing (eg, COVID19, RSV and influenza),
 - Pneumococcal testing (eg, BinaxNOW urine test),
 - Antibiotic resistance results for pneumococcal isolates
 - Sputum Gram stain results
- Hospitalization data:
 - Dates of discharge
 - ICU stay (yes/no)
 - Number of days in ICU
 - Mechanical ventilation and days of ventilator use
 - Requirement for new/increased haemofiltration
 - Non-invasive ventilation requirement and days of usage
- Vital status at Day 30 after enrolment:
 - Deceased, not recovered, recovered, recovered with sequelae, recovery ongoing, unknown
 - Date of death if under 30 days from admission
- Record final clinical/standard-of-care diagnosis for qualifying acute LRTD illness:
 - CAP – radiologically or clinically confirmed, acute bronchitis/LRTI, exacerbation of underlying chronic respiratory disease, LRTI not otherwise specified, congestive cardiac failure, empyema/lung abscess, non-infective process, and non-respiratory infection-related diagnosis.
- Cardiac complications through Day 30 after enrolment:

- ST- and non-ST elevation myocardial infarction, cerebrovascular accident, new episode of atrial fibrillation or other arrhythmia, venous thromboembolism, cardiovascular-related death
- Hospital related adverse events (e.g., falls in hospital and hospital-acquired infections)

The Principal Investigator or designee should make an assessment of final standard-of-care LRTD-related diagnosis if any discrepancy exists in the record. The Investigator is to also confirm, based on any existing or new information, if the participant had clinically and radiographically confirmed pneumonia.

8.3 Non-Consented arms Patient Outcomes: One-year mortality assessment on Day 365

The assessment may be completed 365 to 390 days after enrolment by medical record review, during a follow-up standard care visit and/or other means.

At day 365 after admission, the following will be assessed and recorded in the CRF:

- Vital status (alive or deceased) at Day 365 after enrolment

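### Standard-of-care microbiology has no collection point after Visit 1 in the consented arm, and the tables and text disagree on timing, which weakens the secondary-infection outcome

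*Protocol*

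**What the plan says.** **Consented arm, microbiology.** Section 7.1.1 opens its list with "This will involve collection of the following data at visit 1". The list includes blood cultures, "Respiratory microbiology testing, including bacterial (eg, PCR and culture) and viral testing (eg, COVID19, RSV and influenza"), pneumococcal tests and resistance results. Table 1 marks "Record SOC respiratory specimen testing results", "Record SOC blood culture results" and chest imaging results at Visit 1 only. Its window is 48 hours from admission; section 7.1 asks for enrolment by then where feasible. The Visit 2 lists in 7.2, 7.2.1 and 7.5 cover final diagnosis, vital status, cardiovascular events, research injuries and hospital-related adverse events. They contain no microbiology results.

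**Non-consented arm, microbiology.** The admission list in 8.1.1 leaves microbiology out. Section 8.2 includes it under "At day 30 after admission, the following will be assessed and recorded in the CRF". Table 2 marks the same standard-of-care respiratory and blood-culture rows at the first collection (Day 1) only.

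**Stay and level of care.** Section 7.1.1 lists "Date of hospitalization, length of stay in hospital" at Visit 1, together with discharge date, ICU days, ventilator days, non-invasive ventilation and haemofiltration. Table 1 places "Hospitalization duration, readmission, & level of care" at Visit 2, yet 7.2.1 and 7.5 omit these items. For the non-consented arm, 8.2 and Table 2 both place them at Day 30.

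**Use of the data.** Section 3.2.1 objective 5 concerns COVID-19 and other pathogens, "both with co- and super-imposed infection and secondary respiratory infection". Objectives 6 and 7 use length of stay, ICU stay and ventilation. Section 1.6 says the data of the two arms are combined.

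**The concern.** Superimposed or secondary infection by definition follows the initial illness. In a patient who stays in hospital, much of the evidence for it will come from specimens taken after the first two days. Even a specimen taken on admission may be reported later, particularly for culture and resistance. A schedule that records these results only at a visit within about 48 hours of admission does not suit that outcome.

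There is also a comparability problem. If the consented arm follows Table 1 and 7.1.1 while the non-consented arm follows 8.2, one arm has an early capture of microbiology and the other a 30-day capture. The arms already differ clinically: section 5.1 says that patients missed by consent include early discharges and early deaths. A schedule difference on top of that could not be separated from a real difference once the arms are pooled, and an analysis plan cannot recover results that were never abstracted.

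The stay and organ-support items raise a different question. They cannot be final at Visit 1 for a patient who is still in hospital, so their place in 7.1.1 conflicts with their purpose and with Table 1.

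**Working it through.** The plan states no figure to reproduce; the check is an item-by-item reading of each arm's table against its text.

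| Item | Consented: table | Consented: text | Non-consented: table | Non-consented: text |
|---|---|---|---|---|
| Standard-of-care respiratory and blood-culture results | Visit 1 only (Table 1) | Visit 1 only (7.1.1; absent from 7.2, 7.2.1, 7.5) | Day 1 only (Table 2) | Day 30 (8.2; absent from 8.1.1) |
| Pneumococcal resistance results | no row | Visit 1 (7.1.1) | no row | Day 30 (8.2) |
| Chest imaging results | Visit 1 only | no results item in 7.1.1 or the Visit 2 lists | Day 1 only | no results item in 8.1.1 or 8.2 |
| Stay, ICU, organ support | Visit 2 (Day 30 to 45) | Visit 1 (7.1.1; absent from 7.2, 7.2.1, 7.5) | Day 30 | Day 30 (8.2) |

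Four results follow.

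1. **Consented-arm microbiology.** Table and text agree on Visit 1, and no section adds a later entry. The gap is present whichever of the two governs.
2. **Non-consented microbiology.** Table and text contradict each other. If 8.2 governs, the arms differ. If Table 2 governs, they match, but neither has a later entry and objective 5 is served worse overall.
3. **Stay, ICU and organ support.** In the consented arm the table and text contradict each other. In the non-consented arm they agree on Day 30. If Table 1 governs, both arms are recorded at Day 30 and nothing is lost.
4. **Other provisions that could fill the microbiology gap.**
   - The 30-day information promised for all events in 4.1 is specified as final diagnosis, vital status and cardiovascular complications.
   - Hospital-acquired infections appear at Visit 2 as an example of an adverse event, with no organism, specimen date or resistance result.
   - Residual specimens may be obtained at Visits 2 and 3 and tested for pathogens (6.3.1), where they are available.
   - Section 6.3.2 sends any standard-of-care pneumococcal isolate for confirmation and serotyping, with no visit limit; resistance is not mentioned there.
   - Repeat eligible admissions are expected (4.4.5), and COVID-19 patients are exempt from the 7-day readmission exclusion (4.4.2). A secondary infection that leads to readmission can therefore have its own Visit 1. One arising within the same admission does not.

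What remains is organism, date and resistance detail for later in-hospital tests and for results reported after Visit 1.

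**Size.** Let c be the consented share of patients and p the share of consented patients with a standard-of-care specimen or result after Visit 1. The share affected through the consented arm is c × p. The protocol gives a target of up to 80% for c and nothing for p. With c = 0.80 and p anywhere from 0 to 1, the product runs from 0 to 0.80, which is too wide to be an estimate.

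**The case against.** The strongest reply is that these are visit labels, not data locks. No section sets a specimen or reporting cut-off, and the 48-hour limit is softened in the text. Section 6.2 obtains consent for microbiology outcomes without a time limit. Section 4.4.5 foresees consent after discharge, when the whole admission is already known. Listing resistance results at Visit 1 suggests that staff enter results as they arrive. The Visit 2 review by the investigator can draw on new information when confirming pneumonia.

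Much of this stands. Staff may well back-fill the form, so loss of data is a risk of following the protocol as written, not a demonstrated fact. It does not remove the defect: no document states a later collection point for consented-arm microbiology, and nothing sets a common cut-off for the two arms.

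Three stronger readings are tempting and are not supported.

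- **That microbiology is definitely cut short in one arm relative to the other.** The tables agree between arms; the asymmetry exists only in the text, and nothing says that text overrides tables.
- **That length of stay, ICU and ventilation are truncated at 48 hours for consented patients.** Table 1 schedules stay and level of care at Visit 2, section 11.2 has the database calculate length of admission, and a discharge date cannot be entered for a patient still in hospital.
- **That up to 80% of patients lose results.** That figure is a recruitment target, and only consented patients with a later specimen or a late result could be affected.

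**Conclusion.** The concern holds as a scheduling gap together with two table-text contradictions. In the consented arm, table and text place standard-of-care respiratory and blood-culture results at Visit 1 only, which is too early for the superimposed and secondary infection part of section 3.2.1 objective 5. In the non-consented arm, 8.2 and Table 2 disagree on the timing of the same results. Followed as written, later or late-reported organism, date and resistance results have no scheduled capture in the consented arm, or in either arm if Table 2 governs. Pathogen capture can differ between the pooled arms if 8.2 governs. The placing of stay, ICU and organ-support items in 7.1.1 is a separate contradiction with Table 1; truncation is not established.

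The number of patients affected cannot be derived from the document. The conclusion assumes that sites follow the stated schedule; back-filling would reduce the effect.

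A reader might also infer harm to the primary incidence estimate, because section 9.2.2 lets a positive laboratory test alone classify a patient as having a lower respiratory tract infection. The document does not show how many patients would depend on a late result for that status, and the final clinical diagnosis, another route to it, is assessed at Visit 2. The demonstrated weakness concerns secondary outcomes. This should be fixed, but it does not undermine the study.

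**What to change.** - **Microbiology and imaging.** Add standard-of-care respiratory, blood-culture and chest imaging results, through Day 30 or discharge, to Visit 2 in Table 1 and in 7.2.1 and 7.5, and to the second collection in Table 2. Include pneumococcal resistance results in the text lists. Bring 8.2 into line and state one common cut-off for both arms.
- **Dates.** Record the specimen or imaging date with each result, and use the specimen date to separate infection present at admission from later infection.
- **Stay and organ support.** Move discharge date, length of stay, ICU, ventilation, non-invasive ventilation and haemofiltration from 7.1.1 to 7.2.1 and 7.5, to match Table 1 and 8.2.

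The cost is protocol and case report form wording, plus slightly more abstraction per consented patient at a Visit 2 assessment that already allows record review. No extra patient contact or sample is needed.

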7.2 Consented arm, Visit 2: Final diagnosis/Vital status assessment (Day 30)

The assessment may be completed 30 to 45 days after enrolment by phone call, medical record review, during a follow-up standard care visit and/or other means.

At day 30 after admission, the following will be assessed and recorded in the CRF:

- Record final clinical/standard-of-care diagnosis for qualifying acute LRTD illness
- Vital status (alive or deceased) at Day 30 after enrolment
- Cardiac complications through Day 30 after enrolment

The Principal Investigator or designee should make an assessment of final standard -of-care LRTD-related diagnosis if any discrepancy exists in the record. The Investigator is to also confirm, based on any existing or new information, if the participant had clinically and radiographically confirmed pneumonia.

7.2.1 Data collection at V2:

- Record RRIs
- Hospital-related adverse events (e.g., falls in hospital and hospital-acquired infections)
- Final standard of care/ clinical diagnosis of acute LRTD illness
- Vital status at Day 30
- Occurrence of cardiovascular events within 30 days of illness onset (pneumonia only):

- non-ST elevation myocardial infarction (NSTEMI)
- ST-elevation myocardial infarction (STEMI)
- cerebrovascular accident
- new episode of atrial fibrillation or other clinically significant arrhythmia
- deep venous thrombosis or pulmonary embolism
- new or worsening congestive heart failure
- cardiovascular-related death

7.3 Consented arm, Visit 3 [serology subset only]: Convalescent serology assessment on Day 45

For those enrolled in the Serology subset who have signed the related ICD Annex, a follow-up visit will be conducted approximately 45 days after enrolment (visit window: Day 22 – 60). If there is a low patient return rate for this follow-up visit, the study will consider whether home visits may be more convenient and better suited to patients in this study. If home visits are undertaken, they will be offered to participants as a visit option, and an appropriate time will be arranged after liaison between the participant and research team. The procedures undertaken during home visits will ensure that both study participants and research staff are appropriately protected in line with any Health and Safety regulations (e.g. PPI, sharps bins, etc.).

- Blood specimen for respiratory pathogen serology including RSV will be obtained. An upper respiratory swab will be obtained if intercurrent acute respiratory illness has occurred
- Record RRIs.

7.4 Consented arm, Visit 4: One-year mortality assessment on Day 365

The assessment may be completed 365 to 390 days after enrolment by medical record review, during a follow-up standard care visit and/or other means.

At day 365 after admission, the following will be assessed and recorded in the CRF:

- Vital status (alive or deceased) at Day 365 after enrolment
- If the participant is deceased, total survival days following enrolment

7.5 Consented arm, Patient outcome:

The follow-up information should be collected 1 month after enrolment or when the patient is discharged from hospital (whichever occurs later). At day 30 after admission, the following will be assessed and recorded in the CRF:

- Record final clinical/standard-of-care diagnosis for qualifying acute LRTD illness:
 - CAP – radiologically or clinically confirmed, acute bronchitis/LRTI, exacerbation of underlying chronic respiratory disease, LRTI not otherwise specified, congestive cardiac failure, empyema/lung abscess, non-infective process, and non-respiratory infection-related diagnosis.
- Vital status at Day 30 after enrolment:
 - deceased, not recovered, recovered, recovered with sequelae, recovery ongoing, unknown
- Cardiac complications through Day 30 after enrolment:
 - ST- and non-ST elevation myocardial infarction, cerebrovascular accident, new episode of atrial fibrillation or other arrhythmia, venous thromboembolism, cardiovascular-related death

The Principal Investigator or designee will assess final standard -of-care LRTD/COVID-related diagnosis if any discrepancy exists in the record. The Investigator is to also confirm, based on any existing or new information, if the participant had clinically and radiographically confirmed pneumonia.

7.6 Ongoing clinical care

This is an observational epidemiological study collating and recording standard-of-care investigations and patient details in a consented study with enhanced diagnostic tests. As such, Avon CAP should not impact on any aspect of clinical care or other interventional trial in which the patient may be participating.

7.6 Safety Reporting

This is a minimal-risk, low-interventional study; however, certain safety reporting obligations must be met. Some of these reporting requirements are reported into the clinical study database via the CRF and others must be reported directly to Pfizer as well. A summary is below, and more detail is provided in sections 7.6.1 and in the Safety Reporting Reference Manual.

1. During the 15 minutes after the study-required sample collection, all adverse events (AE)/serious adverse events (SAEs) that occur in that 15 minutes will be recorded in the study database. This is called the “active collection period”.
2. Medically important research related injuries (RRIs) (SAEs related to study participation) will be recorded in the study database only. These do not need to be reported to the Pfizer Drug Safety Unit (DSU), but should be reported to the Pfizer clinical/medical team upon awareness and may also need to be reported to other oversight entities as required by local or institutional regulations.
3. This study does not involve the administration of vaccines or other drugs. However, any SAE that is related to receipt of the Pfizer-BioNTech COVID-19 vaccine, BNT162b2, that the PI/site becomes aware of will be reported to Pfizer DSU within 24 hours of awareness, or immediately if life threatening.
4. Exposures to BNT162b2 during pregnancy will not be reported to the Pfizer DSU as individual case reports unless there is an associated SAE.
5. Lack of Effectiveness (LOE) of BNT162b2 will not be reported as individual SAE reports, since this is a study endpoint and will be tabulated in the clinical study report (CSR).
6. Any reporting requirements described above are not intended to replace reporting obligations to other institutional, local, or regional entities. The reporting required by Pfizer or this study protocol does not take the place of these other obligations.

